APPENDIX 5 Scoring the CHQ-PF50

The CHQ-PF50 provides information on various health concepts, as well as the PhS and PsS scales. Details for scoring each of these concepts and scales are based on the CHQ scoring and interpretation manual ([HealthActCHQ, 2013](#)).

Global Health Item

The global health item (item 1.1) of the CHQ-PF50 is calculated using the steps below.

1. The scores for this item are recoded as presented below, where missing scores remain missing.

Table 12 Scoring of Global Health Item

Response	Precoded Item Values	Final Item Values
Excellent	1	5
Very Good	2	4.4
Good	3	3.4
Fair	4	2.2
Poor	5	1

2. The final scores are then transformed so that they range from 0 to 100 in the following way:

$$(\text{Final item value} - 1) / 4 \times 100$$

Physical Function

Items 2.1 (a to f) are included in this health concept. Each item is coded with a value from 1 to 4, where 1 corresponds to a response “Yes, limited a lot”, 2 “Yes, limited some”, 3 “Yes, limited a little“ and d 4 corresponds to the response “No, not limited”.

The score for the physical function health concept is calculated using the following steps:

1. The mean of the scores (raw score) for items 2.1 (a to f) is calculated if at least 3 of the items have been answered. If less than 3 items have responses this concept is set to missing.
2. The standardized score which ranges from 0 to 100 is then calculated as follows:

$$(\text{Raw score} - 1) / 3 \times 100$$

Role/Social Limitations Due to Emotional or Behavioral Difficulties

This health concept is based on items 3.1 (a to c). Each item is coded with a value from 1 to 4, where 1 corresponds to a response “Yes, limited a lot” and 4 corresponds to the response “No, not limited”.

The steps below are followed to score this health concept

1. If at least 2 of the 3 items have been answered, the mean of the scores (the raw score) for items 3.1 (a to c) is calculated, otherwise this concept is set to missing.
2. The standardized score which ranges from 0 to 100 is then calculated as follows:

$$(\text{Raw score} - 1) / 3 \times 100$$

Role/Social Limitations Due to Physical Health

Items 3.2 (a and b) are included in this health concept. Each item is coded with a value from 1 to

4, where 1 corresponds to a response “Yes, limited a lot” and 4 corresponds to the response “No, not limited”.

The steps below are followed to score this health concept

1. The raw score is calculated as the mean of the scores if at least 1 of the items has been answered, otherwise this concept is set to missing.
2. The standardized score which ranges from 0 to 100 is then calculated as follows:

$$(\text{Raw score} - 1) / 3 \times 100$$

Bodily Pain and Discomfort

The Bodily Pain and Discomfort scale includes items 4.1 and 4.2. The scores for these items are to be reversed as presented in [Table 13](#) and [Table 14](#).

Table 13 Scoring of Item 4.1 for Bodily Pain and Discomfort

Item 4.1 Response	Precoded Item Values	Final Item Values
None	1	6
Very mild	2	5
Mild	3	4
Moderate	4	3
Severe	5	2
Very severe	6	1

Table 14 Scoring of Item 4.2 for Bodily Pain and Discomfort

Item 4.2 Response	Precoded Item Values	Final Item Values
None of the time	1	6
Once or twice	2	5
A few times	3	4
Fairly often	4	3
Very often	5	2
Every/almost every day	6	1

The Bodily Pain and Discomfort scale score is then calculated as follows:

1. The mean of the two scores (the raw score) is calculated if at least one of the items has been answered.
2. The standardized score which ranges from 0 to 100 is then calculated as follows:

$$(\text{Raw score} - 1) / 5 \times 100$$

Behavior

Items 5.1 (a to e) and 5.2 are included in this health concept. Items 5.1 (a to e) are coded with a value from 1 to 5, where 1 corresponds to a response “Very often”, 2 to “Fairly often”, 3 to “Sometimes”, 4 to “Almost never”, and 5 corresponds to the response “Never”.

Responses to item 5.2 are recoded using the rules in [Table 15](#).

Table 15 Scoring of Behavior

Response	Precoded Item Values	Final Item Values
Excellent	1	5
Very Good	2	4.4
Good	3	3.4
Fair	4	2.2
Poor	5	1

The following steps are then used to calculate the Behavior concept score:

1. If at least 3 items have been answered the mean is calculated, otherwise this scale is set to missing.
2. The resulting mean, or raw score, is then standardized to range from 0 to 100 as follows:
$$(\text{Raw score} - 1) / 4 \times 100$$

Global Behavior Item

The global behavior item (item 5.2) of the CHQ-PF50 is calculated using the steps below.

1. The scores for this item are recoded as presented below, where missing scores remain missing.

Table 16 Scoring of Global Behavior Item

Response	Precoded Item Values	Final Item Values
Excellent	1	5
Very Good	2	4.4
Good	3	3.4
Fair	4	2.2
Poor	5	1

2. The final score is then transformed to range from 0 to 100 in the following way:

$$(\text{Final item value} - 1) / 4 \times 100$$

Mental Health

Items 6.1 (a to e) are included in this health concept. Each of the items 6.1 (a to d) is coded with a value from 1 to 5, where 1 corresponds to a response of “All of the time” and 5 corresponds to the response “None of the time”. Responses to item 6.1 (e) are reverse scored as indicated in [Table 17](#).

Table 17 Scoring of Mental Health

Response	Precoded Item Values	Final Item Values
All of the time	1	5
Most of the time	2	4
Some of the time	3	3
A little of the time	4	2
None of the time	5	1

If at least 3 of the items 6.1 (a to e) have been answered the raw score is obtained by calculating the mean of the scores. The raw score is then standardized to range from 0 to 100 as follows:

$$(\text{Raw score} - 1) / 4 \times 100$$

Self Esteem

The self esteem scale includes Items 7.1 (a to f) which are reverse scored as presented in [Table 18](#).

Table 18 Scoring of Self Esteem

Response	Precoded Item Values	Final Item Values
Very satisfied	1	5
Somewhat satisfied	2	4
Neither satisfied nor dissatisfied	3	3
Somewhat dissatisfied	4	2
Very dissatisfied	5	1

If at least 3 of the items 7.1 (a to f) have been answered the mean of the scores is calculated. The mean score is then standardized to range from 0 to 100 as follows:

$$(\text{Raw score} - 1) / 4 \times 100$$

General Health Perceptions

Items 8.1 (a to e) and item 1.1 are included in this scale. Items 8.1 (a, c, e) are scored from 1 to 5 where 1 represents the response “Definitely true” and 5 represents “Definitely False”. Items 8.1 (b and d) are reverse scored as is seen in [Table 19](#).

Table 19 Scoring of Global Health Perceptions

Response	Precoded Item Values	Final Item Values
Definitely true	1	5
Mostly true	2	4
Don't know	3	3
Mostly false	4	2
Definitely false	5	1

Finally, responses to item 1.1 are recoded as presented in [Table 13](#).

The general health perceptions scale is then scored using the steps below:

1. If less than 3 of the items 8.1 (a to e) and 1.1 have been answered, this scale is set to missing. Otherwise calculate the raw score by computing the mean of the responses.
2. The raw score is then standardized so that it ranges from 0 to 100 as follows:

$$(\text{Raw score} - 1) / 4 \times 100$$

Change in Health Item

The change in health item (item 8.2) of the CHQ-PF50 is to be reverse scored as displayed in [Table 20](#).

Table 20 Scoring of Change in Health Item

Response	Precoded Item Values	Final Item Values
Much better now than 1 year ago	1	5
Somewhat better now than 1 year ago	2	4
About the same now than 1 year ago	3	3
Somewhat worse now than 1 year ago	4	2
Much worse now than 1 year ago	5	1

This is a categorical scale and thus no transformation is necessary.

Emotional Impact on Parent

This scale includes items 9.1 (a to c) which are to be reverse scored in accordance with [Table 21](#).

Table 21 Scoring of Emotional Impact on Parent

Response	Precoded Item Values	Final Item Values
Not at all	1	5
A little bit	2	4
Some	3	3
Quite a bit	4	2
A lot	5	1

The emotional impact on parent scale score is then calculated as follows:

1. If at least 2 of the items in this scale have been answered, the raw score is obtained by computing the mean of the responses, otherwise this scale is set to missing.
2. The raw score is then standardized so that it ranges from 0 to 100 as follows:

$$(\text{Raw score} - 1) / 4 \times 100$$

Time Impact on Parent

Items 9.2 (a to c) are included in the time impact on parent scale. The responses range from 1 to 4 where 1 corresponds to “Yes, limited a lot” and 4 corresponds to a response of “No, not limited”. If at least 2 items in this scale have been answered the raw score is calculated as the mean of the items. If less than 2 items have been answered the scale is set to missing.

Finally, the standardized score which ranges from 0 to 100 is calculated as

$$(\text{Raw score} - 1) / 3 \times 100$$

Family Activities

The family activities health concept is comprised of items 9.3 (a to f). The responses range from 1 to 5 where 1 represents the response “Very often” and 5 the response of “Never”. If at least 3 items in this scale the raw score is calculated as the mean of the responses, otherwise the scale is sent to missing.

The raw score is then standardized as:

$$(\text{Raw score} - 1) / 4 \times 100$$

Family Cohesion Item

The family cohesion health concept includes item 9.4 which is recoded using the rules outlined in [Table 22](#).

Table 22 Scoring of Family Cohesion Item

Response	Precoded Item Values	Final Item Values
Excellent	1	5
Very good	2	4.4
Good	3	3.4
Fair	4	2.2
Poor	5	1

The score is then transformed so that it ranges from 0 to 100 as follows:

$$(\text{Raw score} - 1) / 4 \times 100$$

Standardized Physical Summary and Standardized Psychosocial Summary

The PhS and PsS scales are scored using norm-based methods based on data from the general U.S. population and six clinical samples of children. [Table 24](#) includes the sample means and standard deviations, as well as factor score coefficients, used to derive the PhS and PsS scale scores.

Table 24 Information Required for Scoring PhS and PsS Scales

CHQ-PF50 SCALE*	MEAN	SD	FACTOR SCORE COEFFICIENTS	
			PhS	PsS
PF	90.8525408	16.3826344	.37138	-.09243
RP	91.4951246	18.9079749	.34493	-.06973
GH	66.6958379	19.3564297	.29460	-.05547
BP	78.6833515	20.7355708	.27883	-.05514
REB	90.4013015	19.5067502	-.01178	.21155
PT	83.8816188	20.2901603	.09113	.16944
PE	73.9788476	21.406013	.06063	.19823
SE	79.2555314	17.8308361	-.09480	.24792
MH	77.2595806	13.6861999	-.08263	.25335
BE	72.3086051	17.1447913	-.12675	.27911

Note: PF = Physical Functioning; RP = Role/Social-Physical; GH = General Health Perceptions; BP = Bodily Pain; REB = Role/Social Emotional/Behavioral; PT = Parental Impact-Time; PE = Parental Impact-Emotional; SE = Self Esteem; MH = Mental Health; BE = Behavior

The steps used in calculating PsS and PhS are summarized below:

1. Calculate each of the CHQ-PF50 scales presented in Table and using the methods outlined in this appendix.
2. Each scale is then standardized using a z-score transformation as follows:

$$\frac{\text{scale score} - \text{mean of scale}}{\text{std deviation of scale}}$$

where the mean and standard deviation for each scale are obtained from [Table 24](#)

3. Calculate PhS and PsS as a weighted sum of each standardized scale, using the factor score coefficients from Table 24 as the weights for each item in each scale.
4. Transform each scale score to obtain t-score with a mean of 50 and standard deviation of 10 as follows:

$$\text{PhS} = \text{PhS weighted sum} \times 10 + 50$$

$$\text{PhS} = \text{PhS weighted sum} \times 10 + 50.$$

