8.5.2 Patient Quality of Life Questionnaire

This instrument is a well-validated general QoL measure in pediatric populations with chronic illness. It measures QoL of the child and the family by parent or child report. The caregiver will be asked to complete the questionnaire on behalf of the patient. The CHQ-PF50 covers multidimensional health concepts including Physical Functioning, Role/Social Limitations–Emotional/Behavioral, Role/Social Limitations– Physical, Behavior, Mental Health, Self-Esteem, General Health , Bodily Pain, Family Activities, Parent Impact–Time, Parent Impact–Emotional, and Family Cohesion. Scores for specific items and subscales, as well as a standardized physical summary (PhS) score and a standardized psychosocial summary (PsS) score, can be calculated from the CHQ-PF50 questionnaire. Scores are based on a 0 to 100 scale and higher scores indicate better quality of life.

Table 7 presents the items included in each health concept.

Table 6 CHQ-PF50 Health Concepts

Health Concept	Items Included
Global health item	1.1
Physical functioning	2.1 (a to f)
Role/social limitations due to emotional/behavioral difficulties	3.1 (a to c)
Role/social limitations due to physical health	3.2 (a to b)
Bodily pain and discomfort	4.1 and 4.2
Behavior	5.1 (a to e) and 5.2
Global behavior item	5.2
Mental health	6.1 (a to e)
Self esteem	7.1 (a to f)
General health perceptions	8.1 (a to e) and 1.1
Change in health item	8.2
Emotional impact on parent	9.1 (a to c)
Time impact on parent	9.2 (a to c)
Family activities	9.3 (a to f)
Family cohesion item	9.4

Details regarding the scoring of the health concepts of CHQ-PF50 and of the PhS and PsS can be found in [Appendix 5](#). All of the health concepts and scales included in CHQ-PF50, except for the

change in health item are continuous.

CHQ-PF50 standardized scores (as per [Appendix 5](#)) CHQ-PF50 subscale scores, PhS and PsS scores along with their change from baseline (RCT Baseline and OLE Baseline) will be summarized by visit.

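### Two CHQ-PF50 scoring rules in SAP Appendix 5 are misprinted: item 1.1 is sent to a bodily-pain recode, and the PsS T-score line is missing

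*SAP*

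**What the plan says.** Both places are in SAP Appendix 5.

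**Item 1.1.** Under Global Health Item, item 1.1 has its own recode, Table 12, titled "Scoring of Global Health Item". Responses from Excellent to Poor become 5, 4.4, 3.4, 2.2 and 1. The same item is also one of the six in General Health Perceptions, with 8.1 a to e. There the text says "Finally, responses to item 1.1 are recoded as presented in" Table 13. That table is titled "Scoring of Item 4.1 for Bodily Pain and Discomfort"; it has six levels, from None to Very severe, with final values 6 down to 1. The General Health section then gives the scale a range of 0 to 100, obtained by subtracting 1 from the item mean, dividing by 4 and multiplying by 100.

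**PsS.** Step 3 of the summary-score section says "Calculate PhS and PsS as a weighted sum of each standardized scale, using the factor score coefficients from Table 24 as the weights". Step 4 says "Transform each scale score to obtain t-score with a mean of 50 and standard deviation of 10 as follows" and then prints the PhS formula (weighted sum × 10 + 50) twice. There is no PsS formula. SAP Section 8.5.2 commits to reporting both: "PhS and PsS scores along with their change from baseline (RCT Baseline and OLE Baseline) will be summarized by visit".

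**The concern.** These are scoring rules that a programmer will code from, not background text. The Table 13 reference cannot be right alongside the stated range: a divisor of 4 and a 0 to 100 scale require every item to lie between 1 and 5, and Table 13 goes up to 6. An error in General Health also passes into PhS, where that scale carries a coefficient of 0.29460. PsS is one of the instrument's two summary scores, and its final formula is not written down.

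**Working it through.** **Inputs, all from SAP Appendix 5**

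- Table 12 (item 1.1): precoded 1 to 5 become 5, 4.4, 3.4, 2.2, 1.
- Table 13 (item 4.1): precoded 1 to 6 become 6, 5, 4, 3, 2, 1.
- General Health = (mean of answered items − 1) / 4 × 100. The items are 8.1 a to e (final values 1 to 5) and 1.1, and at least three must be answered.
- Table 24, General Health row: SD 19.3564297, PhS coefficient 0.29460, PsS coefficient −0.05547.
- T-score: weighted sum × 10 + 50.

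**1. The plan's stated range, using Table 12.** Best responses: (30/6 − 1)/4 × 100 = 100. Worst: (6/6 − 1)/4 × 100 = 0. This reproduces 0 to 100.

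**2. The range as printed, using Table 13 on the precoded values.** Best: (31/6 − 1)/4 × 100 = 104.17. Worst: (7/6 − 1)/4 × 100 = 4.17. The stated range is not reproduced.

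**3. Shift by response, six items answered.** General Health shift = (Table 13 value − Table 12 value)/6/4 × 100. PhS shift = General Health shift / 19.3564297 × 0.29460 × 10.

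| Item 1.1 response | Table 12 | Table 13 | Difference | General Health shift | PhS shift |
|---|---|---|---|---|---|
| Excellent | 5 | 6 | 1.0 | +4.17 | +0.63 |
| Very Good | 4.4 | 5 | 0.6 | +2.50 | +0.38 |
| Good | 3.4 | 4 | 0.6 | +2.50 | +0.38 |
| Fair | 2.2 | 3 | 0.8 | +3.33 | +0.51 |
| Poor | 1 | 2 | 1.0 | +4.17 | +0.63 |

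PsS moves the other way and very little: 4.17/19.3564297 × (−0.05547) × 10 = −0.12 at most.

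**4. What remains in a change score.** If both visits are scored with the same wrong recode, the shifts partly cancel. The most that can remain is 4.17 − 2.50 = 1.67 General Health points, or 0.63 − 0.38 = 0.25 PhS points.

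**5. Fewer items answered.** With the permitted minimum of three, item 1.1 among them, the shift is 0.6/3/4 × 100 = 5.0 to 1/3/4 × 100 = 8.33 General Health points, and up to 8.33/19.3564297 × 0.29460 × 10 = 1.27 on PhS. SAP Section 6.1.6 says that the electronic form does not let the caregiver skip a question, so six items is the case to plan for.

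**6. How often the score passes 100.** With six items answered, the item sum must exceed 30. Only the pattern with all best responses does so: 1 of 5^6 = 15,625 possible patterns.

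**7. PsS.** Step 3 yields two weighted sums, and step 4 in words applies to each scale score. With the intended line, ten scales at 100 give a PsS weighted sum of 1.405, hence 1.405 × 10 + 50 = 64.05. Without it the reported value would be 1.405, and any change would be one tenth of its T-score size.

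**The case against.** The case for leaving this alone is that the intended reading can be recovered from the SAP in both places.

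- **Table 13 looks like a stale number.** The RSBQ table in Section 8.1.1 is captioned Table 4, as is the CSHQ table, and the RSBQ table is absent from the List of Tables. Counting it moves every later table up by one. The text follows that count when it cites Table 5 for CSHQ, Table 6 for SF-36 and Table 7 for the CHQ-PF50 concepts, whose captions read 4, 5 and 6. On that count the Global Health Item table is Table 13. This explains the reference well. It does not remove the problem, because the bodily-pain section of the same appendix cites Tables 13 and 14 as captioned, so a reader cannot apply one offset throughout.
- **The mismatch would probably be noticed.** Table 13 carries a pain title and pain labels, and item 1.1 runs from Excellent to Poor. The shifts above require mapping the raw codes while ignoring title, labels and stated range. That stands as a reason to think the error unlikely to survive programming, but a scoring appendix should not rely on it.
- **Step 4 already gives the PsS rule in words.** This stands. A reader might infer that PsS will not be produced, or will be reported around 0 where 50 was meant. The documents do not support that: step 4 covers each scale score, and Section 8.5.2 commits to reporting PsS. Also, 0 and 50 are norm-sample means, and nothing in the plan says that patients with Rett syndrome would average either. PhS and PsS differ by one letter, so the printed line should be checked against the sponsor's SAP file.
- **The endpoint is exploratory and descriptive.** This stands and limits the weight of the point.

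**Conclusion.** Both rules are wrong as printed, and the impact is minor. The Table 13 reference contradicts the scale's stated range. If followed literally with six items answered, it raises General Health by 2.50 to 4.17 points and PhS by 0.38 to 0.63 for every respondent, with at most 1.67 and about 0.25 points left in a change score. Those sizes assume that precoded values are mapped without regard to the response labels and that both visits are scored alike.

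The PsS omission is a formula misprint with a clear intended reading. It produces a wrong score only if the printed lines are coded without the sentence above them.

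A reader might also expect General Health values above 100 in the tables. With complete forms only one response pattern in 15,625 gives that; the upward shift and the floor of 4.17 are the more general effects. CHQ-PF50 is an exploratory endpoint summarized without hypothesis testing, so no primary safety conclusion depends on either error.

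**What to change.** Make two edits in SAP Appendix 5:

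1. Under General Health Perceptions, change the item 1.1 reference from Table 13 to Table 12.
2. In step 4 of the summary scores, change the second line to PsS = PsS weighted sum × 10 + 50.

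Then check the scoring program against both. Two test records suffice: all best responses to the six General Health items must give exactly 100, and all ten scales at 100 must give PhS 58.44 (0.844 × 10 + 50) and PsS 64.05. The cost is two lines of text and a short program check; no data collection or analysis changes.
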